7.6 Flow chart

7.7 Data collection

All baseline and outcome data will be collected prospectively using a data collection form. This data form has been designed to collect all clinical and procedural information (see Annex 7) from the different NICUs participating in this project.

Each patient will be identified with a special ID to maintain anonymity, the patient's name cannot appear. Once a week, the neonatologist expert or hospital coordinator of each hospital must collect all the files gathered by the neonatologists of his/her hospital and add them to an online database. When the statistical specialist analyses the database, he/she will not know the name of the baby, or the technique used.

A data quality control service will be contracted to supervise the process and ensure correct data collection.

Period 1: Inclusion and baseline data

The main investigator will contact potential participants to evaluate if they meet all the inclusion criteria and any exclusion criteria. This will take place in the NICU, when there is a preterm infant with NRDS on invasive mechanical ventilation.

If the patient meets all the study criteria, an information form (see Annex 4) and an informed consent (see Annex 5) will be given to the parents after proper explanation.

When the patient is already part of the study, the researcher will proceed with the collection of baseline data, corresponding to the covariates.

Period 2: Intervention period

A baseline researcher, not involved in the outcome assessment, will be responsible for assigning the ID code to each participant. In addition, this

researcher will distribute to the neonatologist the randomised allocation prepared by the biostatistician, indicating the protocol he/she will use.

During the intervention, the baseline researcher must ensure that all dependent variables related to the intervention are collected.

Period 3: Follow up

After 72 hours of the intervention, the baseline researcher not involved in the outcome assessment will evaluate the dependent variable (reintubation).

Once completed, the data form must be sent to the hospital coordinator or neonatologist expert who will add the data to the general online database.

Later, when all the data from all the participants is completed, it will be sent to the statistician expert for analysis.

Figure 18 - Summary of the data collection process

7.8 Safety

The intervention carried out in this study does not entail any added risk to the patient, as all patients on invasive mechanical ventilation require the weaning process prior to extubation.

In this study, the intervention focuses only on the assignment of the weaning protocol. The two protocols used in the trial are those currently used in NICUs, with studies that support their use.

So, patients on the study will not have any additional risk compared to patients in the same situation outside the study.

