3.2.10 Complications

Acute complications of positive pressure ventilation or invasive mechanical ventilation include air leak syndromes such as pneumothorax, pneumomediastinum, and pulmonary interstitial emphysema.

Bronchopulmonary dysplasia (BPD) is a chronic complication of RDS. Its pathophysiology, clinical presentation and management are discussed in section 3.1.5.

Another complication can be neurodevelopmental delay, especially in infants who have had prolonged mechanical ventilation. The incidence of cerebral palsy is also increased in infants with RDS, with the incidence decreasing with increasing gestational age. The duration of mechanical ventilation correlates with increased rates of both cerebral palsy and neurodevelopmental delay.(37)

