3.3.3. Invasive mechanical ventilation

There are a lot of different modalities of invasive mechanical ventilation.

Only the two modalities related to this project will be discussed: **assist-control volume guarantee ventilation** and **pressure-support ventilation**.

Assist-control ventilation

Assist-control volume guarantee ventilation (ACVGV) is a combination mode of ventilation in which the **current tidal volume is delivered in response to the inspiratory effort or if no patient effort occurs within a set period of time**. The period is determined by the backup respiratory rate set on the ventilator. When there is an inspiratory effort from the patient, the ventilator senses this as a trigger and initiates another controlled breath.

All breaths are done by the ventilator, the patient cannot take spontaneous breaths. (53)

The advantage of ACV (assist-control ventilation) is that it significantly reduces work of breathing and decreases myocardial oxygen demand. The disadvantages of ACV in the active patient are that it is less comfortable than spontaneous breathing and that it can induce respiratory alkalosis and breath-stacking.

With volume ACV, the volume is set by the professional, so it is constant, but the airway pressure varies. When patients with severe hypoxaemia require high PEEP and FiO₂ settings to maintain adequate oxygenation, the airway pressures that are generated to deliver the desired tidal volume increase. This increasing pressure can be measured as the peak inspiratory pressure or the plateau pressure, all of which attempt to describe the pressures that are transmitted through the airways at different levels and at different points in the respiratory cycle. (49)

[figure not shown]

Figure 12 - Assist-control ventilation curves (54)

Pressure support ventilation

Pressure support ventilation (PSV) is used in patients who are awake enough to breathe spontaneously. It augments the patient's spontaneous inspiratory efforts with the selected level of positive airway pressure. (49) The ventilator does not do any of the breathing, the patient starts all the breaths, and the ventilator helps with each one with a certain pressure. The **beginning and end of the breaths are therefore determined by the patient's effort.** (53)

Inspiratory pressure is delivered until the flow decreases to a predetermined level (usually 25% of peak flow). PSV allows the clinician to control the desired pressure support, PEEP, and FIO₂.

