7.3 Sampling

7.3.1 Sample size

We estimated the sample size using the free online software GRANMO, and the setting for two independent proportions.

In the view of the literature published so far, the proportion of reintubation in preterm newborns that are on invasive mechanical ventilation is 16% (studies differ between 12% and 20%, an average has been made).(62,63)

Accepting an alpha risk of 0.05 and a beta risk of 0.2 in a two-sided test, **271** subjects are necessary in first group and **271** in the second to recognize as statistically significant a difference greater than or equal to 0.1 percent units. A proportion in one of both groups has been estimated to be 16%. It has been anticipated a drop-out rate of 5% (0,05).

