7.4 Variables and measurements

Independent variable

The independent variable is the **invasive mechanical ventilation protocol** used during the weaning. It is conceived as a **dichotomous qualitative nominal variable** and is expressed as PSV/ACVGV:

- PSV: Pressure support ventilation
- ACVGV: Assist control volume guarantee ventilation

Dependent variables

There are two dependent variables: **number of reintubations** and **time of weaning**.

The **number of reintubations** is the main dependent variable. It is a **discrete quantitative variable**. The higher the number of reintubations, the higher the risk of complications, so it is a good variable to determine which protocol is more effective. Extubation failure is defined as reintubation within 24-72 hours, so the number of reintubations will be counted for the first 72 hours after the extubation.

The **time of weaning** is the secondary dependent variable. It is a **continuous quantitative variable**. It is counted from the moment the weaning is started until the extubation is executed. The longer this time is, the greater the risk of complications arising from invasive ventilation that the child may have, so it is a good variable to determine which protocol is more effective.

Covariates

- **Gestational age at birth/type of preterm:** once is born, the baby will be classified into one of these categories. It is a *dichotomous qualitative ordinal variable*:
 - Extremely preterm (< 28 weeks of gestation)
 - Very preterm (28-32 weeks of gestation)
- **Birthweight:** it is a *continuous quantitative variable* measured in grams.
- **Sex:** it is a *dichotomous qualitative nominal variable*. Categorized as men or women.
- **CPR after birth:** it is a *dichotomous qualitative nominal variable*. It will be expressed as yes or no.

- **5-minute Apgar score** (see Annex 1): It is a quantitative variable, but categorized in the following intervals, resulting in a *polychotomous qualitative ordinal variable*:
 - Apgar 0-3
 - Apgar 4-6
 - Apgar 7-10
- **Risk factors of prematurity:**
 - **Previous preterm birth:** it is a *dichotomous qualitative nominal variable*. It will be expressed as yes or no.
 - **Second trimester miscarriage (> 16 weeks):** it is a *dichotomous qualitative nominal variable*. It will be expressed as yes or no.
 - **Multiple pregnancy:** it is a *dichotomous qualitative nominal variable*. It will be expressed as yes or no.

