The autonomy of the participants is regulated by Spanish legislation: “**Law 41/2002, November 14th, regulating patient autonomy and right and obligations of information and clinical documentation**”. (66)

Privacy and confidentiality

All personal data collected from each patient during the study will be confidential, only for purpose of research and education; moreover, all data will be analysed anonymously, in accordance with the current legislation:

- Spanish data protection legislation: “**Organic Law 3/2018, of 5 December, on Data Protection and Guarantee of Digital Rights and the royal decree 1720/2007**”. (67)
- ***Regulation (EU) 2016/679 of the European Parliament and of the Council of 27 April 2016 on the protection of natural persons regarding the processing of personal data and on the free movement of such data.*** (68)

All newborns personal and clinical data collected in this study will be anonymous and confidential, as they will be identified by a **randomised code** generated by an electronic randomisation statistical software.

In addition, all data collected will **be available only to the research team** and will be used strictly for research purposes.

Comité d'Ètica i d'Investigació Clínica (CEIC)

The present project will be submitted to the CEIC of the *Hospital Universitari [name] (HUJT)*, whose suggestions given will be considered and whose approval will be mandatory before the start of the study. The system of controls to be carried out during the research will be in accordance with **Ley 14/2007, de 3 de julio, de Investigación biomédica**. (69)

Transparency

All investigators of this study will be required to declare no conflicts of interest. They will also have to agree to publish all data and results obtained with total transparency, including unfavourable data or events.

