- 6. Formation sessions** (April 2024): An online meeting will be held with the whole team to provide theoretical training on neonatal resuscitation and neonatal mechanical ventilation. Particular emphasis will be placed on invasive mechanical ventilation and weaning. During this meeting, a consensual and detailed document will be sent to the hospital coordinators of each centre with the values of each parameter of the ventilator necessary for both the initiation of weaning and extubation. It will also include the clinical and gasometrical criteria for weaning, extubation and reintubation.

The aim of this training is to homogenise the process and reduce differences in the results between centres.

- 7. Creation of a database** (April 2024): A computer scientist will be hired to create a database, so that the data collected before, during and after the intervention can be correctly recorded.

STAGE 3: Sample recruitment, intervention, and data collection (27 months: May 2024 – July 2026)

8. Sample recruitment: As mentioned above, a consecutive stratified sampling method of extremely and very preterm newborns with NRDS that are on invasive mechanical ventilation, admitted to the NCIU of the participating hospitals will be carried out. Each co-investigator at each centre will be responsible for enrolling patients who meet all the inclusion criteria and any of the exclusion criteria, after the parents or legal guardians have signed the informed consent form (see Annex 5). Each participant will be randomised to one of the intervention groups of the clinical trial. The hospital coordinators of each centre will supervise this process.

Recruitment will continue until each centre has recruited the number of participants assigned by the stratification, with a 1:1 ratio. This is expected to take approximately 26 months (2 years and 2 months).

9. Intervention: During this period, patients will be assigned to one of the protocols for weaning, PSV in one arm of the study and ACVGV in the other.

This process can take a few days or even a few weeks, so an extra month has been added to the projected 26 months for this stage.

10. Follow up: After the intervention, all patients enrolled in the study will be followed for the first 72 hours after extubation, as all clinical data will be recorded in the baby's medical record.

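### Section 7.8 says the intervention adds no risk, but apart from reintubation and weaning time the plan records no harm for comparison by arm, not even death

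*Combined protocol and SAP*

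**What the plan says.** Section 7.8 (Safety) opens by denying that the intervention adds risk. Its grounds are that every ventilated infant has to be weaned and that both modes are already used in NICUs. It ends: "So, patients on the study will not have any additional risk compared to patients in the same situation outside the study". Section 14 (Feasibility) then relies on this absence of added risk when it predicts that parents will agree readily.

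Other sections treat the choice of mode as consequential:

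- Section 5.1 expects fewer reintubations with PSV than with ACVGV.
- Section 7.4 says "The higher the number of reintubations, the higher the risk of complications".
- Section 3.3.3 says of assist-control ventilation in the active patient that "it can induce respiratory alkalosis and breath-stacking", and says of PSV that it does not guarantee a tidal volume.
- Section 3.2.10 says the acute complications of positive pressure or invasive ventilation "include air leak syndromes such as pneumothorax, pneumomediastinum, and pulmonary interstitial emphysema".

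On data, section 7.4 and Table 4 define two dependent variables, number of reintubations and time of weaning, and sections 8.2 and 8.3 analyse those two. The intervention block of Annex 7 has three items: protocol code, reintubation, and weaning time in days. Section 7.2 lists death as a withdrawal criterion. Section 9 (Transparency) commits investigators to publish everything, "including unfavourable data or events". Section 10.3 limits follow-up to 72 hours after extubation, "as all clinical data will be recorded in the baby's medical record".

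**The concern.** That both modes are in use shows they are accepted, not that they carry equal risk. Section 4 itself says no studies show which is better for these infants. What the trial adds to usual care is random assignment of the mode, and the trial is built on the premise that mode changes how often an infant is reintubated. The opening sentence of 7.8 is therefore more absolute than the rest of the protocol supports.

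The practical consequence lies in the data. Section 4 says a superior protocol could be implemented. If one mode gives fewer reintubations or shorter weaning but more air leak or more deaths, the planned dataset would not show it. The duty in section 9 to publish unfavourable events has no planned data collection behind it, even though the information will already be in the chart.

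**Working it through.** **1. The plan's own sample size.** Inputs from section 7.3.1: "Accepting an alpha risk of 0.05 and a beta risk of 0.2 in a two-sided test"; "A proportion in one of both groups has been estimated to be 16" per cent; a difference of 0.1, read as 10 percentage points; drop-out 5%.

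Unpooled formula for 16% against 26%:

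n = (1.96 + 0.8416)² × (0.16 × 0.84 + 0.26 × 0.74) / 0.10² = 7.849 × 0.3268 / 0.01 = 256.5, so 257 per arm.

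257 / 0.95 = 270.5, so 271 per arm and 542 in total. This is the plan's figure. Using 16% against 6% gives 150, or 158 after drop-out, which does not match.

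**2. What that difference means in infants.** 0.10 × 271 = 27.1. The plan is sized to detect about 27 more reintubated infants in one arm than in the other, for an event it links to complications.

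**3. Harms named, set against data planned.**

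| Harm | Where named | On Annex 7 | Compared by arm in section 8 |
|---|---|---|---|
| Reintubation | 7.4 | yes | yes |
| Longer weaning | 7.4 | yes | yes |
| Alkalosis, breath-stacking (assist-control) | 3.3.3 | no | no |
| Tidal volume not guaranteed (PSV) | 3.3.3 | no | no |
| Air leak (ventilation in general) | 3.2.10 | no | no |
| IVH, BPD (prematurity; BPD also tied to ventilation) | 3.1.5, 3.2.10 | no | no |
| Death | 7.2, as withdrawal only | no | no |

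Blood gas values appear in section 7.5 as extubation and reintubation criteria, but they are neither on the form nor in the analysis.

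**4. What 542 infants could show if harms were abstracted.** The documents give no rate for air leak or death in this population during the trial window, so the rates below are assumptions.

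Half-width of the 95% interval for a difference, equal rates: 1.96 × √(2p(1 − p)/n).

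At p = 0.05: n = 271 gives 1.96 × √(0.095/271) = 0.0367; n = 257 gives 1.96 × √(0.095/257) = 0.0377.

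Power to detect a doubling (two-sided 5%, normal approximation, pooled variance under the null) uses n = 257:

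| Assumed rate | Half-width, n = 271 | Half-width, n = 257 | Power for a doubling |
|---|---|---|---|
| 1% | ±1.7 points | ±1.7 points | 15% |
| 2% | ±2.4 | ±2.4 | 26% |
| 5% | ±3.7 | ±3.8 | 58% |
| 10% | ±5.1 | ±5.2 | 89% |

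At 1%, with two or three expected events per arm, the approximation is rough. With no events in 257 infants, the one-sided 95% upper bound is 1 − 0.05^(1/257) = 1.2%.

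**5. Which harms fit the existing follow-up.** Air leak and death can be counted from randomisation to 72 hours after extubation. For IVH, section 3.1.5 places nearly all bleeding in the first week and most of it within 24 to 48 hours. Randomisation waits until weaning criteria are met (section 7.5), so many bleeds may precede it; a grade before randomisation is needed to separate them. BPD is judged at 36 weeks postmenstrual age (section 3.1.5). For an infant born before 32 weeks that is more than 36 − 32 = 4 weeks after birth, so it would generally fall outside the 72-hour window.

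**The case against.** The strongest reply is that the closing sentence of 7.8 compares participants with similar infants outside the study, who receive the same two modes. A difference between arms does not imply excess risk over usual care. This stands: a reader might infer that the sentence is flatly contradicted, and it is not. The tension is with the opening sentence of 7.8 and with the lack of data to test either statement.

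Four other strong readings also go too far.

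- That no named harm is captured. Reintubation and weaning time are collected by arm, and section 7.4 ties both to complications.
- That the protocol describes air leak, BPD and IVH as differing by mode. Air leak and BPD are tied to ventilation generally, and IVH to prematurity. Only alkalosis with breath-stacking, and the unguaranteed tidal volume, belong to one mode. That the others may differ by mode is a reasonable inference, not a statement in the text.
- That the trial's aim is to reduce complications. Section 4 states the aim as fewer reintubations and shorter weaning; complications are the rationale, and adoption is conditional.
- That no problem could surface during the trial. The three-monthly meetings in section 10.3 exist partly to raise problems, and the content of the data manager's interim report is not stated. What is missing is a systematic record by arm.

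It is also fair that the trial is not sized for rare harms, and that BPD would lengthen follow-up when section 12.2 credits the short follow-up for the low expected loss. Neither argues against abstracting events that are already charted within the window.

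**Conclusion.** The point holds in a limited form. Section 7.8 is worded too absolutely for a trial that randomises mode and is sized on about 27 of 271 infants' difference in reintubation. Beyond reintubation and weaning time, the variables, the data form and the analysis contain no harm outcome, and death is only a reason for withdrawal. A mode could be adopted with no planned comparison of other harms.

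The primary comparison can still be run, so this is a worthwhile and cheap improvement rather than a fatal defect. A reader might infer that no mode should be called superior until BPD or IVH is known. The documents do not support that: these are not trial outcomes, the sample was not chosen for them, and the intervals would leave moderate differences unresolved.

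The precision and power figures rest on assumed event rates and on 257 to 271 infants per arm. The conclusion about missing data rests on section 7.4, Table 4, section 8 and Annex 7. The information sheet and consent form are not in the review copy and are not relied on.

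**What to change.** 1. Reword section 7.8 to say that both modes are in current use, but that allocation may change the risk of reintubation and of other ventilation complications. Align section 14 and check the parent information for the same claim.
2. Add to Annex 7, copied from the medical record: air leak (yes or no, date) and death (date), each from randomisation to 72 hours after extubation; and, where routine ultrasound exists, IVH grade before randomisation and at the end of follow-up.
3. Add to section 8 one table giving each of these by allocated arm, with the difference and its 95% confidence interval, labelled as descriptive safety outcomes.
4. Treat BPD at 36 weeks postmenstrual age as optional. It needs oxygen exposure and respiratory support data well beyond 72 hours, with possible transfers or discharges to trace.

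Pooled counts in an interim report would not serve instead, since they cannot show a difference between arms.

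Cost: a few abstraction fields per infant and one table, with no new procedure, staff role or change to 542. The drawback is low power for rare harms (26% for a doubling from an assumed 2%), so the absence of a visible difference should not be reported as evidence of equal safety.

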8. STATISTICAL ANALYSIS

The analysis of the data obtained will be done by a **statistical analyst**, who will not know in which group PSV protocol was used and in which ACVGV protocol. The software used will be *Statistical Package for Social Sciences (SPSS)* software version 28.1. A p-value of $< 0,05$ will be considered statistically significant, defining a 95% confidence interval for all analyses.

8.1. Descriptive analysis

First, we will summarize all dependent, independent variables and covariates.

- **Qualitative variables** (protocol used, type of preterm, CRP after birth, 5-minute Apgar score and most covariates related with risk factors) will be described using **proportions**.
- **Quantitative variables** (number of reintubations, time of weaning, birthweight, maternal age, and maternal size) will be summarized by **means, standard deviation, medians, and interquartile range (IQR)**

The dependent variables are quantitative, so a comparison of medians will be made in relation to the assigned protocol, PSV or ACVGV, will be done. These descriptives will be stratified by the categories of the covariates.

